4.3.3 Point of Enrollment

Given that the prospective study population consists of patients who are already selected for flow diversion therapy and that the screening assessments consist of standard patient diagnostics for this therapy, subjects are considered enrolled in the study once the subject has signed and dated the Informed Consent or DRF and the Pipeline™ Flex Embolization Device with Shield Technology™ is advanced into the micro catheter inside the subject.

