6 ADVERSE EVENTS

The following Adverse events will be collected during the course of the study on the eCRFs.

- All Adverse Events (AE) with an underlying neurological cause (Neurological Adverse Events)
- All Device Related Adverse Effects
- All Procedure Related Adverse Events
- All Bleeding Events
- All Serious Adverse Events (SAEs)

Adverse event status will be evaluated throughout the study. These will include events occurring from the point of enrollment until a subject exits the study. If the subject is enrolled and the study procedure is attempted, but the Pipeline™ Flex Embolization Device with Shield Technology™ is not implanted for any reason, subjects will be followed to discharge and relevant safety events will be collected. Investigators must obtain all information available to determine the causality and outcome of the AE and to assess whether it meets the criteria for classification as a serious and/or

unexpected event requiring notification to the Sponsor, and, where applicable, regulatory agency and IRB/EC, within the specified reporting timeframe. AEs will be categorized using the definitions in **Section 6.1**.

All study AEs, as well as the treatment and follow-up required, should be documented in the subject's medical records and in the eCRF. All study SAEs that occur during the 1 year follow-up period will be followed by the investigator until resolution or until 30 days after the occurrence of that event. A list of potential anticipated adverse events is provided in **Section 10.2**.

Bleeding events will be captured as Adverse Events by the sites and will be graded according to the GUSTO⁴⁴ bleeding criteria as seen in

Table 6-1 by the Clinical Events Committee.

Table 6-1. GUSTO Bleeding Criteria

GUSTO Bleeding Category	Definition
Severe or Life-Threatening	Intracerebral hemorrhage Substantial hemodynamic compromise requiring treatment
Moderate	Requiring blood transfusion but not resulting in hemodynamic compromise
Mild	Bleeding that does not meet the above criteria

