21 DEFINITIONS

TERM	DEFINITION
Adverse Event (AE)	
Any untoward medical occurrence, unintended disease or injury, or untoward clinical signs (including abnormal laboratory findings) in subjects, users or other persons, whether or not related to the investigational medical device. (ISO 14155:2011 3.2)
 
Note 1: This definition includes events related to the investigational medical device or the comparator.
 
Note 2: This definition includes events related to the procedures involved.
 
Note 3: For users or other persons, this definition is restricted to events related to investigational medical devices.

Adverse Device Effect (ADE)	
An adverse event related to the use of an investigational medical device. (ISO 14155:2011 3.1)
 
Note 1: This definition includes adverse events resulting from insufficient or inadequate instructions for use, deployment, implantation, installation, or operation, or any malfunction of the investigational medical device.
 
Note 2: This definition includes any event resulting from use error or from intentional misuse of the investigational medical device.

Device Migration	
Movement of one or more Pipeline™ Flex Embolization Device with Shield Technology™ of more than 5 mm in its parent artery location in comparison to the post-placement angiogram.

Device-related Adverse Effect	
Event has a strong temporal relationship to the study device, and alternative etiology is less likely.

TERM	DEFINITION
Procedure	The primary study procedure involving the placement of the Pipeline™ Flex Embolization Device with Shield Technology™ at Day 0.
Neurological Adverse Event	An adverse event with an underlying neurological cause.
Neurological Death	Subject death due to neurologic reasons.
Point of Enrollment	Once the subject has signed and dated the Informed Consent or DRF, point at which the Pipeline™ Flex Embolization Device with Shield Technology™ is advanced into the micro catheter inside the subject.
Procedure-related Adverse Event	Event has a strong temporal relationship to the procedure (Day 0). This includes AEs attributable to any device(s) other than the Pipeline™ device used at procedure (Day 0), such as access devices, delivery microcatheters, non-ionic contrast, guidewires, or any other adjunctive, approved/cleared device for treatment of intracranial aneurysms.
Retreatment	Any subsequent intervention (post study procedure with Pipeline implant) performed to treat the target IA.

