The primary objective of this study is to assess the *outcomes* of the Pipeline™ Flex Embolization Device with Shield Technology™ in patients undergoing treatment for intracranial aneurysms in a large real-world, post-market setting. *Outcomes* will be assessed based on a series of standardized measurements recorded during the procedure and during the post-procedure follow-up period.

Attributes and parameters to characterize the outcomes of the Pipeline™ Flex Embolization Device with Shield Technology™ during the procedure will be addressed based on the following assessments (as observed):

- Successful deployment of the study device to the target site
- Implantation of the study device
- Entire IA neck covered by the study device
- Device malfunction during the delivery system preparation
- Adverse Events: By seriousness (Serious or Non-Serious) peri-procedural (Day 0), by relatedness (Procedure, Device and Anti-platelet therapy)

Attributes to characterize the outcomes of the study device post-procedure will be addressed based on the following assessments:

- Aneurysm occlusion (Class 1: Complete obliteration, Class 2: Residual neck, or Class 3: Residual Aneurysm)
- Adverse events: By Seriousness (serious and non-serious) ; per relatedness (procedure, device or antiplatelet therapy) and time of event (Acute 1-30 days, and Delayed 31-Study exit)
- Modified Rankin Scale (mRS)
- NIH Stroke Scale (NIHSS)
- Retreatment
- Major stroke in the territory supplied by the treated artery or neurological death
- Delayed Intracerebral hemorrhage (ICH) > 30 days post-procedure
- Parent artery stenosis (per Core Lab)
- Device migration (per Core Lab)

5. Investigation Plan

A prospective, single-arm, multi-center post-market observational study.

Up to 200 subjects who meet the Inclusion/Exclusion Criteria may be enrolled over a period of approximately 2 years to reach a target number of subjects. Study participation includes initial screening

and baseline evaluation, treatment using the Pipeline™ Flex Embolization Device with Shield Technology™, and follow-up visits at the discretion of the treating physician for 1 year beyond the index procedure. The total study duration is expected to be approximately 3 years.

Study Design:

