7.2.1 Analysis Conventions

Specific algorithms are discussed for imputing missing or partially missing dates, if deemed appropriate, under specific data topics. Imputed or derived data will be flagged in the individual patient data listings. Imputed data will not be incorporated into any raw or primary datasets. These data are retained in derived (or analysis) datasets.

The term *Primary Study Procedure* refers to the initial study procedure, *Re-treatment Procedure* refers to the treatment performed after the *Primary Study Procedure*.

Total duration on study will be calculated as the difference between the date of procedure (Day 0) and the last on-study observation. All calculations defining the duration on study will be performed relative to the date of procedure and follow the algorithm $DURATION = [STUDY\ COMPLETION\ OR\ WITHDRAW\ DATE - PROCEDURE\ DATE]$.

Post-procedure angiograms will be reviewed to assess aneurysm occlusion according to the scale of Roy:

- Complete = Complete occlusion, no flow of contrast seen in the aneurysm sac
- Residual Neck = Partial occlusion, some flow or eddying flow in the aneurysm sac
- Residual Aneurysm = Incomplete occlusion, apparent flow in the aneurysm sac

Procedure time will be calculated based on the following sentinel events. Start Time: Time of skin incision. End Time: skin closure

Major Stroke: A stroke, in which the NIHSS of the subject increases by ≥ 4 and persists for 7 days and more.

Minor Stroke: A stroke, which resolves completely within seven days OR increases the NIHSS of the subject by ≤ 3 .

Neurological Death is any patient death due to neurological reasons.

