7.7 Treatment Characteristics

Procedure characteristics, study device usage and procedure imaging information will be summarized using descriptive statistics for continuous variables (mean, median, standard deviation, number of observations, minimum and maximum) and frequency tables for discrete variables.

Pipeline™ device STUDY PROCEDURE with Shield Technology™ and Efficacy

This section will discuss the tabulation and analysis of the study procedure, type and size of the Pipeline™ device with Shield Technology™ and follow-up. Detailed descriptions of the statistical procedures that will be used to analyze the study variables will be described below.

In the design of the outcome data from this registry, a collective approach has been used to compile the results within an overall summary table. Given there is clinical interest to examine multiple variables for the various populations, this approach has been adopted. Separate subset tables may be extracted for discussion for the overall summary table.

Study Procedural Characteristics

The summarization of the procedural data for the ITT population will be presented in a table entitled Summary of the Primary Study Procedure Characteristics; a similar table will be restricted to the ICA population. The term Primary Study Procedure refers to the initial procedure, given the patient may require re-treatment.

Time of skin incision to time of first Pipeline™ device with Shield Technology™ introduction will be calculated and presented in minutes. The time of first Pipeline™ device with Shield Technology™ introduction to last Pipeline™ device with Shield Technology™ delivery system removal will be calculated and presented in minutes. Time of skin incision to time of skin closure will be calculated and presented in minutes. Cumulative flouro time will be summarized for the ITT population in minutes. The time interval data described above will be summarized using descriptive statistics: n, arithmetic mean, standard deviation, median, range (i.e., minimum and maximum values). Subjects with missing data that cannot be resolved prior to database lock will not be included in the tabulation and excluded from the summary statistics; all data will be presented in a listing.

The information collected and to be summarized and reported in the listings is presented below:

[REDACTED]

[REDACTED]

- [REDACTED]
- [REDACTED]

[REDACTED]

[REDACTED]

[REDACTED]

[REDACTED]

[REDACTED]

[REDACTED]

[REDACTED]

- [REDACTED]

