 - Access Site Complications
 - Procedural Systemic Complications
 - Vasospasms
- Neurological Events:
 - Focal Neurological Deficit
 - Cerebral Infraction
 - Transient Ischemic Attack (TIA)
 - Intracranial Hemorrhage (ICH)
 - Stroke
 - Death

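### Protocol section 6 opens adverse-event collection part-way through the Day 0 procedure, which contradicts the documents' own definition and reporting of procedure-related and access-site events

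*Protocol*

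**What the plan says.** Protocol section 6 lists the categories to be collected, among them "All Procedure Related Adverse Events", all bleeding events and all serious adverse events. It then gives the time span: "These will include events occurring from the point of enrollment until a subject exits the study". No other sentence in the protocol or SAP states when adverse-event collection opens.

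Protocol 4.3.3 and section 21 define enrollment as signed consent or data release form, plus the point at which the study device "is advanced into the micro catheter inside the subject". The SAP repeats this definition in sections 3 and 5.

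Other places reach further back into the procedure:

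- Protocol section 21, on procedure-related adverse events: "This includes AEs attributable to any device(s) other than the Pipeline™ device used at procedure (Day 0), such as access devices, delivery microcatheters". It goes on to name contrast and guidewires.
- SAP 7.2.1, on procedure time: "Start Time: Time of skin incision".
- SAP 7.7: "Time of skin incision to time of first Pipeline™ device with Shield Technology™ introduction will be calculated". The interval before the device appears is thus a measured part of the procedure.
- SAP 7.9 lists "Access Site Complications", procedural systemic complications and vasospasm among the events of interest.
- SAP 7.10 places adverse events in a peri-procedural category defined as Day 0, and SAP 7.13.2 names serious adverse events on Day 0 as an analysis.

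**The concern.** The only stated opening of the window falls after some of the events it is meant to capture. A vessel dissection, wire perforation, vasospasm or contrast reaction can occur between skin incision and device introduction. It would meet the definition of a procedure-related event, yet precede the stated window, even in a subject who is then enrolled and implanted.

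A site reading the sentence as a limit would leave such events out, while a site reading the category list would enter them. Later steps would not repair the difference. Under Protocol 8.1 the Clinical Events Committee reviews the events reported in the study, so it does not restore an event that was never entered. The SAP classifies timing by date, so a Day 0 table would not show which sites had included the earlier part of the procedure.

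At stake are the Day 0, procedure-related and access-site rates. SAP section 3 intends to contrast results with earlier Pipeline studies and use them for, among other purposes, a US indication evaluation.

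**Working it through.** The plan derives no figure from the collection window, so there is none to reproduce. The check is a comparison of passages, followed by an illustration of size.

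**Order of events on Day 0**

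1. Skin incision: procedure clock starts (SAP 7.2.1).
2. Arterial access, then placement of the microcatheter. Complications here are procedure-related (Protocol section 21).
3. Device advanced into the microcatheter: enrollment (Protocol 4.3.3), and the adverse-event window opens (Protocol section 6). The microcatheter must already be inside the subject, so step 2 always comes first.
4. Attempted deployment: entry to the ITT population (SAP section 5).
5. Skin closure: procedure clock stops (SAP 7.2.1).

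The procedure-related definition and the Day 0 category cover steps 1 to 5. The literal window covers only step 3 onward. The mismatch is steps 1 and 2.

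**Size per missed subject**

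N = 200 attempted deployments (SAP section 5). One subject whose event is not entered lowers a subject-level rate by 1/200 = 0.5 percentage points.

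**Primary safety against the 15% threshold**

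SAP section 6 reads the 1-year rate with a two-sided 95% Clopper-Pearson interval. For x events in n subjects the upper limit is the 0.975 quantile of a Beta(x + 1, n − x) distribution. With n = 200, the largest x whose upper limit is below 15% is 19 (19/200 = 9.5%, interval 5.8% to 14.4%).

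The following illustration uses observed counts and ignores imputation. Both the 11 counted events and the number missed are assumptions.

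| Missed events in enrolled subjects | True count | Rate | Upper limit |
|---|---|---|---|
| 0 | 11 | 5.5% | 9.6% |
| 1 | 12 | 6.0% | 10.2% |
| 2 | 13 | 6.5% | 10.9% |
| 4 | 15 | 7.5% | 12.1% |
| 6 | 17 | 8.5% | 13.3% |

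From 11 counted events, 20 − 11 = 9 would have to be missed before the upper limit was no longer below 15%.

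**The case against.** The strongest reply is that the sentence in section 6 is worded inclusively, not restrictively. The same section requires all procedure-related, bleeding and serious events. Table 5-1 lists adverse events for the procedure period as a whole, and the SAP schedule of assessments places them in the Procedure (Day 0) column. The missing-date rule in SAP 7.10 turns on the start of the study procedure, and no SAP rule uses the time of device introduction to exclude an event. The eCRF guidelines, the committee charter and the Safety Management Plan, which are not available here, may settle site practice.

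Most of this stands. It shows that the documents intend to capture early Day 0 events, and that leaving them out is one reading rather than the only one. It does not remove the conflict. A span with a start and an end is naturally read as a limit, and the category list carries no time rule of its own.

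Four stronger inferences a reader might draw are not supported:

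- *That early Day 0 complications are in fact excluded from the safety data.* The passages just listed point the other way, so the finding is a contradiction and not a demonstrated loss.
- *That any stroke beginning before device introduction falls outside the primary endpoint.* A major stroke needs an NIHSS rise of at least 4 that is still present after seven days. In an enrolled subject the deficit therefore persists into the window, and a later neurological death also falls inside it. What remains is the risk that a site judging by onset does not enter the event.
- *That "Device malfunction during the delivery system preparation" is also lost.* Device-specific events come under Protocol section 7, which requires all of them to be reported and sets no enrollment-based start.
- *That the downward bias can be quantified, or shown relative to earlier Pipeline studies.* The documents give neither the share of events arising before device introduction nor those studies' collection windows.

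**Conclusion.** The contradiction is real and should be corrected. Taken literally, the stated window omits the access and navigation part of a procedure whose complications the documents define as procedure-related and plan to report. If some sites apply it literally, Day 0, procedure-related and access-site rates will be too low, and a navigation-related stroke could go unentered.

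The direction follows from the text, but the size does not: it depends on how many sites take the literal reading and how many events start before device introduction, and neither is given. The main effect is on the procedural adverse-event tables. A reversal of the primary safety reading against 15% is unlikely, given the margin up to 19 events in 200.

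**What to change.** In Protocol section 6, state that for every subject who becomes enrolled, adverse events are collected from the start of the Day 0 procedure, defined as skin incision, to study exit. Keep the enrollment point unchanged for deciding who is in the study. In SAP 7.10, state that the peri-procedural (Day 0) category uses the same start.

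The cost is one sentence in the protocol, a matching line in the SAP and an update to the eCRF completion guidelines. Consent or the data release form is a condition of enrollment, and the operative record is already source material. The downside is a slightly higher reported procedural event rate.

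This change does not reach consented patients whose procedure is abandoned before the device is advanced. Under Protocol 5.6 they are screen failures with only the reason recorded, which is a separate matter for the sponsor to consider.

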5.6 Screen Failure

Subject will be considered a screen failure if:

- The subject signs the informed consent or DRF but fails to meet study inclusion/exclusion criteria during the screening and baseline phase.
- The subject signs the informed consent or DRF, meets the study inclusion/exclusion criteria but an attempt to implant the Pipeline™ Flex Embolization Device with Shield Technology™ is not performed.

Subjects that undergo consent but are screen failures will be exited from the study and will not be required to undergo any additional follow-up. Only the reason for subject screen failure will be recorded.

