9.3 Analysis Population

The primary analysis sample will be based on the principle of intention-to-treat (ITT). All enrolled subjects who underwent the study procedure and in whom an attempt to implant the device was made will be included in the analysis population.

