Stroke	
A focal neurological deficit of presumed vascular origin persisting more than 24 hours from symptom onset AND a neuro-imaging study or other quantitative study that does not indicate a different etiology.
 
The 24-hour criterion is excluded if the subject undergoes cerebrovascular surgery or dies during the first 24 hours of symptom onset.
 
The definition includes subjects presenting with clinical signs and symptoms suggestive of subarachnoid hemorrhage, intracerebral hemorrhage, or cerebral infarction. The definition also includes sudden loss or worsening of visual acuity due to retinal artery occlusion or retinal emboli.
 
The definition excludes slowly progressive cranial nerve palsies or progressive visual field deficits due to continued aneurysm growth. The definition also excludes stroke events in cases of blood disorders such as leukemia or external events such as trauma.
 
Stroke severity will be graded by the CEC as major or minor:
 
Major Stroke: A stroke, which is present after seven days and increases the NIH Stroke Scale of the subject by ≥ 4.
 
Minor Stroke: A stroke, which resolves completely within seven days OR increases the NIH Stroke Scale of the subject by ≤ 3.
 
Each major stroke will further be categorized, with respect to:
 
 - Event was caused by thromboembolic events - Event was caused by side-branch occlusion due to the study device
Unanticipated Serious Adverse Device Effect (USADE)	
A serious adverse device effect which by its nature, incidence, severity or outcome has not been identified in the current version of the risk analysis report. (ISO 14155:2011 3.42)
 
Note: Anticipated serious adverse device effect (ASADE) is an effect which by its nature, incidence, severity or outcome has been identified in the risk analysis report.

Neurological Death	Any subject death due to neurological reasons.
Transient Ischemic Attack (TIA)	Transient Ischemic Attack is defined as neurological deficit symptoms lasting ≤ 24 hrs with no evidence of cerebral infarction on imaging.
Cerebral Infarction	Cerebral Infarction is defined as evidence of new ischemic changes (infarction) on imaging with no associated symptoms or symptoms lasting ≤ 24 hours.

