ICH	International Conference for Harmonization	An Organization whose main purpose is to achieve greater harmonization to ensure that safe, effective, and high-quality medicines are developed and registered in the most resource-efficient manner.
IDE	Investigational Device Exemption	An approved IDE permits a device that would otherwise be required to comply with a performance standard or would require a premarket approval to be shipped lawfully for the purpose of conducting investigations of that device (21 CFR 812).
I/E	Inclusion/Exclusion Criteria	A list of conditions that would include or exclude a patient from enrolling/participating in a clinical study as outlined in the study protocol.
Implant Failure	Implant Failure	Enrolled subjects who underwent the study procedure and in whom an attempt to implant the device was made but was unsuccessful

Abbreviation	Abbreviated Term	Definition
IRB	Institutional Review Board	Any board, committee, or other group formally designated by an institution to review biomedical research involving subjects and established, operated and functioning in conformance with 21 CFR 56.
ITT	Intent-to-Treat	The Intention to Treat (ITT) population includes all enrolled subjects in whom deployment of the Pipeline™ device with Shield Technology™ was attempted. It is possible that the Pipeline™ device with Shield Technology™ may not reach the target site and the operator would not attempt to deploy it, in the rare event that happens, that patient will not be considered part of the ITT population.
MedDRA	Medical Dictionary for Regulatory Activities	Standardized medical terminology developed by ICH to facilitate sharing of regulatory information internationally for medical products used by humans. It is used for registration, documentation and safety monitoring of medical products both before and after a product has been authorized for sale. Products covered by the scope of MedDRA include pharmaceuticals, vaccines and drug-device combination products.

Abbreviation	Abbreviated Term	Definition

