Subjects will be considered enrolled in the study once the patient has signed and dated the Informed Consent or DRF and the Pipeline™ Flex Embolization Device with Shield Technology™ is advanced into the micro catheter inside the patient. All enrolled subjects who underwent the study procedure and in whom an attempt to implant the device was made will be included in the analysis population.

A CEC will be in place for the study using a minimum of three physicians knowledgeable in the appropriate disciplines and medical specialties pertinent to the disease state being evaluated in this clinical study. This committee will be responsible for the review and adjudication to the study variables of all events identified in the CEC Charter/Manual of Operations.

The CEC will independently adjudicate to specified endpoint event definitions, event relatedness, event severity, and event outcomes.

The imaging core laboratory will be responsible for the qualitative image analysis to determine aneurysm occlusion, parent artery stenosis, and device migration. An imaging protocol will be provided to the site.

Pre-Specified Study Endpoints:

The pre-specified study endpoints and analysis listed here are the primary body of data that will be collected, analyzed, and summarized in a series of tables, lists, and graphs as part of the final report for this study. Other analysis will be conducted as part of the final report but these are the core set of analyses that will constitute the foundation of the clinical study report.

Primary endpoints:

Safety:

- Occurrence of major stroke in the territory supplied by the treated artery or neurological death post-procedure (1-year)

Effectiveness:

- Complete aneurysm occlusion (defined as Raymond-Roy grade 1) without significant parent artery stenosis ($\leq 50\%$) or retreatment of the target aneurysm post-procedure (1-year)

Secondary endpoints:

Safety:

- Occurrence of major stroke in the territory supplied by the treated artery or neurological death at 30 days post-procedure due to procedural complications
- Delayed intracerebral hemorrhage > 30 days post-procedure

Effectiveness:

- Device deployment success rate at the target site

Additional Safety Analyses:

- [REDACTED]
- [REDACTED]

- [REDACTED]
 - [REDACTED]
 - [REDACTED]

Additional Effectiveness Analyses:

- [REDACTED]
 - [REDACTED]
 - [REDACTED]
- [REDACTED]
- [REDACTED]
- [REDACTED]
- [REDACTED]
- [REDACTED]

Study Procedure:

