Subjects will be considered enrolled in the study once the patient has signed and dated the Informed Consent or DRF and the Pipeline™ Flex Embolization Device with Shield Technology™ is advanced into the micro catheter inside the patient. Per each site’s standard of care procedure, at screening, each patient can undergo a neurologic examination and assessment using the mRS and NIHSS, blood draw for hematocrit, platelet count, platelet function testing, serum creatinine, and a pregnancy test (if applicable). Pertinent medications taken by the study participant starting on the day of study procedure were collected while for platelet reactivity start date can also be > 30 days before procedure (in case patient was already under antiplatelet, including anticoagulants and antiplatelet therapy). Subjects will be assessed and documented at baseline. Patient eligibility assessment is to be performed based on data available to the investigator at the time of screening. Patient will be considered a screen failure if:

- The patient signs the informed consent or DRF but fails to meet study inclusion/exclusion criteria during the screening and baseline phase.
- The patient signs the informed consent or DRF, meets the study inclusion/exclusion criteria but an attempt to implant the Pipeline™ Flex Embolization Device with Shield Technology™ is not performed.

The investigator will assess device occlusion, device placement and overall status of the aneurysm. At the investigator’s discretion, the target IA may be retreated at any time during the study. In such situations, the date of the initial procedure (and not the date of the retreatment) will be considered Day 0.

If the target IA undergoes an attempted deployment with the Pipeline™ device with Shield Technology™ but is not implanted or receives an alternate treatment (e.g., coils), the patient is considered an implant failure and will be followed up until hospital discharge. However, if the target IA does not undergo an attempted deployment with the Pipeline™ device with Shield Technology™ and is not treated or receives an alternate treatment (e.g., coils) during the initial procedure, the patient is considered a screen failure and no further follow up is required.

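### Subjects with a failed implant count in the 30-day and 1-year safety endpoints but are followed only to hospital discharge, so their later endpoint events are not collected

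*Protocol*

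**What the plan says.** **Who is analysed.** Protocol 9.3 bases the primary analysis on enrolled subjects who had the procedure and "in whom an attempt to implant the device was made will be included in the analysis population". The ITT definition in SAP section 2 "includes all enrolled subjects in whom deployment of the Pipeline™ device with Shield Technology™ was attempted". The same list defines implant failures as enrolled subjects who had the procedure and "in whom an attempt to implant the device was made but was unsuccessful". Membership turns on the attempt, so implant failures are in ITT. SAP 7.1.3 and 7.9 make ITT the primary population.

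**What is measured.** The primary safety endpoint is major stroke in the treated territory or neurological death at 1 year. The first secondary safety endpoint is "Occurrence of major stroke in the territory supplied by the treated artery or neurological death at 30 days post-procedure due to procedural complications" (SAP sections 5 and 7.9).

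**How long they are followed.** Protocol section 6: if the procedure is attempted but the device "is not implanted for any reason, subjects will be followed to discharge and relevant safety events will be collected". SAP section 5, Study Procedure: "the patient is considered an implant failure and will be followed up until hospital discharge". Under Estimated Duration of Patient Participation, the same SAP section says that each study patient has 1 year of follow-up.

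**How incomplete follow-up is treated.**
- SAP 7.4 applies multiple imputation to the 1-year primary safety endpoint for event-free subjects who do not complete follow-up. A separate observed-data tabulation counts early withdrawals without an event as non-events.
- SAP 7.2 presents event rates as x/N, with N the size of the analysis population.
- SAP 7.9 lets missing data shrink the denominator. Its example is 98/196 with an ITT population of 200.

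**The concern.** The endpoints run to 30 days and 1 year, but for one subset of the primary population observation is planned to stop at discharge. No planned contact would pick up a stroke or neurological death that occurs later in these subjects. They are the subjects in whom the device could not be placed, so their outcomes are part of an attempt-based safety rate.

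The analysis rules do not clearly repair the gap. One group may be imputed, counted as event-free or dropped from the denominator, depending on which SAP section is applied. The SAP introduction says that the results may support a US indication evaluation, and SAP section 6 sets the 1-year safety rate against a 15% threshold. Both the missing events and the choice of rule should therefore be settled.

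**Working it through.** The documents give no expected implant-failure rate and no formal sample size calculation, so there is no design figure to reproduce.

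**Inputs**
- N = 200 attempted deployments (SAP section 5).
- Reference event rate: 6/107 = 5.6% major ipsilateral stroke or neurologic death at 180 days, from the earlier pivotal study cited in Protocol 1.2.3.
- Implant-failure rate: assumed 2-5%, so k = 4 to 10 subjects. The nearest figure in Protocol 1.2.3 is 46 of 47 braids placed (97.9%). That is a per-device figure, so it guides the assumption but does not estimate it.
- Two-sided 95% Clopper-Pearson limits and the 15% threshold (SAP section 6).

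**Expected missed events** = k × p; bias = k × p / N; P(at least one missed) = 1 − (1 − p)^k.

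| k | k × 0.056 | bias (percentage points) | P(at least one) |
|---|---|---|---|
| 4 | 0.22 | 0.11 | 0.21 |
| 10 | 0.56 | 0.28 | 0.44 |

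At this risk these are upper estimates, because 5.6% is a full 180-day rate and includes early events that in-hospital follow-up would catch. Each missed event moves the rate by 1/200 = 0.5 points.

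**Effect of the analysis rule.** Take 11 observed events (5.6% of 200 is 11.2) and k = 10.
- Failures counted as event-free: 11/200 = 5.5%, upper limit 9.6%.
- Failures dropped: 11/190 = 5.8%, upper limit 10.1%.
- Every unfollowed failure counted as an event: 21/200 = 10.5%, upper limit 15.6%.

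With k = 4 the last case is 15/200 = 7.5%, upper limit 12.1%.

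**Distance to the threshold.** 19/200 = 9.5% has an upper limit of 14.4%; 20/200 = 10.0% has an upper limit of 15.02%. One event can change the comparison with 15%, but only near that boundary. At 5.5% observed, it takes about 10 failures that all have events.

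**What imputation can do.** No implant failure has planned 1-year follow-up, so the imputation model has essentially no observed 1-year outcomes from that group. It must borrow their post-discharge risk from implanted subjects. No imputation is stated for the 30-day endpoint.

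**The case against.** **The primary analysis already handles incomplete follow-up.** This stands in part. Multiple imputation is the main presentation (SAP 7.2.2 and 7.4), so a reader who infers that every safety rate is biased downward goes too far. What remains is that the imputation rests on implanted subjects.

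**At 30 days these subjects are not necessarily counted as event-free.** This stands. SAP 7.2 points that way, but SAP 7.9 would drop them. The withdrawal rule in SAP 7.4 does not clearly cover a subject released at discharge as planned. The supportable statement is that the rules conflict. The 30-day endpoint is also limited to procedural complications.

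**Strokes before discharge.** The protocol's definition of major stroke begins "A stroke, which is present after seven days and increases the NIH Stroke Scale of the subject", the SAP schedule has no NIHSS at discharge or day 7, and later NIHSS is optional. A reader might infer that a stroke in a subject discharged early cannot be graded. The documents do not support that. Protocol section 6 follows serious adverse events to resolution or for 30 days, and the Clinical Events Committee may request further documents (Protocol 8.1). Grading is probably possible. The residual defect is that the serious-event rule refers to the 1-year follow-up period and is not reconciled with discharge-only follow-up.

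**Screen failures.** A reader might add enrolled subjects without an attempt to implant, for whom Protocol 5.6 says "Only the reason for subject screen failure will be recorded". The SAP definition places subjects without a deployment attempt outside ITT, so they cannot bias these rates. This is a separate inconsistency.

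**Size and purpose.** The study is observational, has no formal success criteria (Protocol 9.2), and also reports post-procedure results in implanted subjects only. Protocol 1.2.3 reports that in an earlier registry most major events, 12 of 191 subjects, fell within 30 days. These points limit the importance of the gap. They do not remove the mismatch in the primary population, and the stretch between discharge and day 30 is not observed either.

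**Conclusion.** The mismatch is real and appears in both documents: attempted-but-not-implanted subjects are in the primary safety denominator, and their endpoint events after discharge are not collected. The SAP also contradicts its own statement of 1-year follow-up for each study patient.

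The likely bias is downward and small: about 0.1-0.3 percentage points, assuming 2-5% implant failures and the 5.6% reference rate. It would be larger if failures carry higher risk, for which the documents give no figure. It would decide the comparison with 15% only near 19 or 20 events in 200. The 1-year primary analysis is partly protected by imputation. The observed 1-year tabulation and the 30-day rate depend on SAP rules that disagree. This is a cheap improvement that should be made, not a flaw that undermines the study.

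**What to change.** **If follow-up is still open.**
- In Protocol section 6 and SAP section 5, keep every ITT subject, implanted or not, in the existing 1-, 3-, 6- and 12-month contacts for adverse events. No imaging is needed.
- The 1-month contact has a window of ±14 days and can fall before day 30. Let that contact or the next one confirm event status through day 30.
- State that the serious adverse event follow-up rule applies to implant failures. A telephone call yields no NIHSS, so grading will still rely on source documents.

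**If enrollment or follow-up is already complete**, as some past-tense wording in the SAP suggests, the SAP alone can be changed.
- Report the number of implant failures and their observed follow-up.
- Use one stated denominator rule across SAP 7.2, 7.4 and 7.9.
- Add a worst-case safety analysis that counts unfollowed implant failures as events. SAP 7.9 plans worst-case and tipping-point analyses for effectiveness only.

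**Separately**, reconcile the screen-failure wording in Protocol 5.6 and SAP section 5 with Protocol 4.3.3 and section 6, under which a subject is enrolled once the device is advanced into the microcatheter and events are collected from then on. This does not change the ITT rates.

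**Cost.** Amendment wording and up to four calls for each of roughly 4-10 subjects (at most 16-40 calls), with no change in sample size. The reported safety rate may become slightly less favourable.
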